7.13.5. Injection 2 (Day 22) and Injection 3 (Day 43)

7.13.5.1. Before Each Injection

1. Record concomitant medications/procedures (Section 7.14.2)
2. Vital sign measurements (Section 7.14.7)
3. Targeted examination of the affected shoulder including:
 - AROM and PROM (Section 7.14.4.2)
 - ASES function sub-scale (Section 7.14.4.3)
 - ASES pain sub-scale (Section 7.14.4.3)
 - Pain on movement (Section 7.14.5)
4. Urine pregnancy testing
5. Compliance with home exercises
6. Injection site reactions and local tolerability
7. Adverse events (Section 8)

Subjects who are deemed eligible for re-treatment by the investigator will receive study drug under ultrasound guidance after administration of local anesthesia (Section 7.6)

7.13.5.2. After Each Injection

1. Record concomitant medications/procedures (Section 7.14.2)
2. Vital sign measurements (Section 7.14.7)
3. Injection site reactions and local tolerability
4. Adverse events (Section 8)

7.13.6. Day 29 and Day 50 (7 Days After Injection 2 and Injection 3)

The following procedures will be performed on Days 29 and 50:

1. Record concomitant medications/procedures (Section 7.14.2)

2. Vital sign measurements (Section 7.14.7)
3. Examination of affected shoulder including:
 - AROM and PROM (Section 7.14.4.2)
4. Compliance with home shoulder exercises
5. Injection site reactions and local tolerability
6. Adverse events (Section 8)

7.13.7. Follow-up Day 64

The following procedures will be performed on Day 64:

1. Record concomitant medications/procedures (Section 7.14.2)
2. Vital sign measurements (Section 7.14.7)
3. Examination of the affected shoulder including:
 - AROM and PROM (Section 7.14.4.2)
 - ASES function sub-scale (Section 7.14.4.3)
 - ASES pain sub-scale (Section 7.14.4.3)
 - Pain with movement (Section 7.14.5)
4. Compliance with home shoulder exercises
5. Injection site reactions and local tolerability
6. Adverse events (Section 8)

7.13.8. Follow-up Day 95 (End of Study)

The following procedures will be performed on Day 95:

1. Record concomitant medications/procedures (Section 7.14.2)
2. Vital sign measurements (Section 7.14.7)
3. Examination of the affected shoulder including:
 - AROM and PROM (Section 7.14.4.2)
 - ASES function sub-scale (Section 7.14.4.3)
 - ASES pain sub-scale (Section 7.14.4.3)
 - Pain with movement (Section 7.14.5)

4. Collection of samples for:
 - a. Clinical laboratory testing (Section 7.14.10.1)
 - b. Anti-AUX-I and anti-AUX-II antibody testing and neutralizing antibodies to AUX-I and AUX-II (Section 7.14.10.2)
5. Subject satisfaction with treatment (Section 7.14.11)
6. Investigator assessment of improvement with treatment (Section 7.14.12)
7. Injection site reactions and local tolerability
8. Adverse events (Section 8)
9. Discharge from study

7.14. Demographic, Efficacy, and Safety Assessments

7.14.1. Medical History

During the screening period, the investigator or qualified designee will obtain a medical history from each subject that includes relevant diagnoses including past episodes of adhesive capsulitis and procedures/therapies with onset/resolutions dates.

Medical histories should also include history of the current episode of AC including the affected shoulder (right or left), onset date of symptoms, and determination of idiopathic or traumatic AC.

History of tobacco and alcohol use (never, current, former) should also be included.

7.14.2. Prior/Concomitant Medications and Procedures

All prior medications taken within 90 days before randomization will be recorded. All medications (including over-the-counter medications) taken by the subject on Day 1 through the end of the study must be recorded.

Additionally, any diagnostic, therapeutic or surgical procedures performed during the study period should be recorded including the date, indication for and description of the procedure.

7.14.3. Physical Examination

During the screening period, the investigator or qualified designee will perform a physical examination (by body system) on each subject. Height and body weight will be measured and recorded. Hand dominance will be recorded.

7.14.4. Targeted Examination of the Shoulder

7.14.4.1. Inspection

During the screening visit, each subject will have an examination of the affected and unaffected shoulders that will include:

- inspection for swelling and bruising, scars suggestive of old trauma, deformity, and asymmetry
- signs of shoulder instability
- signs of shoulder impingement

7.14.4.2. Active and Passive Range of Motion

During the screening visit, the investigator or qualified designee will measure AROM (performed by the patient), and PROM (performed by the investigator or qualified designee without assistance from the subject), in the affected shoulder and the unaffected shoulder of each subject. AROM will be performed with the subject seated (Appendix A). PROM will be performed with the subject in the supine position (Appendix B). AROM should be performed before PROM. The unaffected arm will be measured with the goniometer first; then the affected arm will be measured with the goniometer second.

Follow-up AROM and PROM measurements of the affected shoulder will be recorded as follows:

- Before each injection, Days 8, 29, 50, 64, and at the Day 95 follow-up visit.

At each time point, the measurement should be repeated a total of three times. For forward flexion, abduction, external rotation, and internal rotation, if the measurements are within 10 degrees of each other, record the highest of the three measurements. If any of the three measurements are greater than 10 degrees of another, the sequence of measurements should be repeated.

The person (ie, investigator or qualified designee) who performs the screening AROM and PROM measurements should, when possible, perform all follow-up measurements for that subject.

7.14.4.3. American Shoulder and Elbow Surgeons (ASES) Patient Self-Evaluation

7.14.4.3.1. Function Sub-Scale

During the screening visit; before injection on Days 22 and 43; and at the Days 64 and 95 follow-up visits, each subject will indicate his/her ability to perform each of the activities listed in Table 3 using the affected shoulder/arm as follows:

‘Circle the number in the box that indicates your ability to do the following activities with your affected shoulder/arm’. Please answer **all** questions.

Table 3: ASES Function Sub-Scale

	Affected Shoulder/Arm			
	0=Unable to do	1=Very difficult to do	2=Somewhat difficult	3=Not difficult
1. Put on coat	0	1	2	3
2. Sleep on your painful or affected side	0	1	2	3
3. Wash back/do-up bra in back	0	1	2	3
4. Manage toileting	0	1	2	3
5. Comb hair	0	1	2	3
6. Reach a high shelf	0	1	2	3
7. Lift 10 lbs (4.5 kg) above shoulder	0	1	2	3
8. Throw a ball overhand	0	1	2	3
9. Do usual work – List:	0	1	2	3
10. Do usual sport – List:	0	1	2	3

Adapted from the American Shoulder and Elbow Surgeons Standardized Shoulder Assessment Form, Patient Self-Evaluation

7.14.4.3.2. Pain Sub-Scale

During the screening visit; before injection on Days 22 and 43; and at the Days 64 and 95 follow-up visits, each subject will circle a number on the 11-point pain visual analogue scale (VAS) that corresponds to his/her response to the following question: 'How bad is the pain in your affected shoulder today'.

0	1	2	3	4	5	6	7	8	9	10
No pain at all										Pain as bad as it can be

Adapted from the American Shoulder and Elbow Surgeons Standardized Shoulder Assessment Form, Patient Self-Evaluation

7.14.5. Pain With Movement

During the screening visit; before injection on Days 22 and 43; and at the Days 64 and 95 follow-up visits, each subject will circle a number on the 11-point pain visual analogue scale (VAS) that corresponds to his/her response to 'How bad is the pain upon movement of your affected shoulder at its worst in the last 24 hours'.

0	1	2	3	4	5	6	7	8	9	10
No pain at all										Pain as bad as it can be

7.14.6. Home Shoulder Exercises

Home shoulder exercises as described in Appendix C should be performed by each subject a minimum of three times a day. Home shoulder exercises will begin one day after Injection 1 and will end on Day 64. Each subject will be provided with a pulley for home exercise use.

7.14.7. Vital Signs

During the screening period, each subject will have blood pressure (systolic/diastolic), respiratory rate, and radial pulse assessed after he/she has been seated upright for at least 5 minutes. Body temperature will also be recorded.

On each injection day, vital signs will be assessed after the subject has been seated upright for at least 5 minutes as shown in Table 4.

Table 4: Vital Signs Measurements – Injection Days

Time point Relative to Injection	Blood Pressure, Respiratory Rate, Radial Pulse	Body Temperature
Up to 4 hours before	X	X
Approximately 15 minutes after	X	
Approximately 30 minutes after	X	
Approximately 45 minutes after	X	
Before discharge from the unit	X	X

Follow-up vital sign measurements, including blood pressure (systolic/diastolic), respiratory rate, and radial pulse, will be assessed after the subject has been seated upright for at least 5 minutes on Days 8, 29, 50, 64, and at the Day 95 follow-up visit.

NOTE: blood pressure should be taken on the non-treated arm.

7.14.8. 12-Lead Electrocardiogram

During the screening period, subjects will have a resting 12-lead electrocardiogram (ECG). A qualified physician will interpret, sign, and date the ECGs. Electrocardiogram assessments must be ‘within normal limits’ or interpreted as ‘abnormal, not clinically significant’ for the subject to be included in the study. ECG findings will be documented as normal; abnormal, clinically significant; or abnormal, not clinically significant. The investigator or qualified designee must sign and date the ECG, thereby acknowledging review of ECG results.

7.14.9. X-Ray and Magnetic Resonance Imaging (MRI) of the Affected Shoulder

During the screening period, subjects will have an x-ray of their affected shoulder to assist in ruling out other clinically significant conditions and clinically significant pathology (eg, glenohumeral arthritis, fracture). Magnetic resonance imaging (MRI) without contrast will be performed during the screening period to assist in ruling out other conditions (eg, subscapularis tendon rupture, rotator cuff injuries). MRI findings at screening will be assessed by the investigator or qualified designee and documented as normal; abnormal, clinically significant;

or abnormal, not clinically significant. Note: Clinically significant MRI findings refer to significant pathological conditions that are distinct from adhesive capsulitis.

X-rays or MRIs of the affected shoulder that were performed within 3 months of the screening visit may be used provided the subject has not experienced a worsening of symptoms during this time period.

Copies of both X-rays and MRIs will be collected as part of the study data. All image data must be de-identified prior to submission to the Sponsor or designee.

7.14.10. Clinical Laboratory and Immunogenicity Testing

Blood (~15 mL) and urine samples will be collected for testing of the following clinical laboratory and immunogenicity parameters.

7.14.10.1. Clinical Laboratory Testing

Clinical laboratory testing as shown in Table 5 will be done at the following time points:

- Screening
- Follow-up (Day 95)

Table 5: Clinical Laboratory Parameters

Hematology	Clinical Chemistry	Urinalysis
Hematocrit	Blood urea nitrogen	Specific gravity
Hemoglobin	Creatinine	Ketones
Red blood cell count	Total bilirubin	pH
Red blood cell morphology	Alanine aminotransferase (ALT)	Protein
White blood cell count	Aspartate aminotransferase (AST)	Blood
Neutrophils	Alkaline phosphatase	Glucose
Lymphocytes	Sodium	
Monocytes	Potassium	
Basophils	Calcium	
Eosinophils	Chloride	
Platelets	Phosphate	
	Serum bicarbonate	
	Uric acid	
	Total cholesterol	
	Total protein	
	Thyroid stimulating hormone	
	Glucose	
	Triglycerides	
	Albumin	

NOTE: Women of childbearing potential (including but not limited to all women ≤55 years of age) will have urine pregnancy testing (dipstick) at screening and before each dose of study drug.

A sponsor-selected central clinical laboratory will process specimens and provide results for each subject. The investigator or qualified designee will evaluate each laboratory value for

CONFIDENTIAL INFORMATION

Auxilium Pharmaceuticals, Inc.
AUX-CC-871-Protocol- 20SEP13

clinical significance. If a laboratory value is outside the reference range for the subject, and the investigator determines it represents a clinically significant change from the baseline or previously assessed value(s), the investigator will make an assessment of drug relatedness and record as an adverse event as appropriate. A subject with a clinically significant laboratory value should be followed until there is a satisfactory resolution of the abnormality, or until the subject's condition has stabilized. Details regarding blood and urine sample collection, processing, and shipping will be provided in a separate Laboratory Manual. The investigator or qualified designee must note clinical significance for abnormal values and sign and date laboratory reports acknowledging review of laboratory results.

7.14.10.2. Anti-AUX-I and Anti-AUX-II Antibodies and Neutralizing Antibodies to AUX-I and AUX-II

Serum samples for the determination of anti-AUX-I and anti-AUX-II antibody testing and neutralizing antibodies to AUX-I and AUX-II will be collected during the screening visit and at the Day 95 follow-up visit.

The serum samples obtained will be stored at -20°C and then shipped on dry ice to the designated clinical laboratory before forwarding to Auxilium Pharmaceuticals, Inc.'s appointed laboratory for the determination of anti-AUX-I and anti-AUX-II antibodies.

Neutralizing antibody plasma samples collected in this study will be stored until the end of the study, at which time a decision for longer term storage will be made. These samples may be analyzed in the future, if needed.

7.14.11. Subject Satisfaction With Treatment

At the Day 95 follow-up visit, each subject will be asked to rate his/her satisfaction with treatment as follows:

1. Very Satisfied
2. Quite Satisfied
3. Neither Satisfied nor Dissatisfied
4. Quite Dissatisfied
5. Very Dissatisfied

7.14.12. Investigator Assessment of Improvement With Treatment

At the Day 95 follow-up visit, the investigator will determine the degree of improvement in the severity of the subject's treated shoulder compared with screening as follows:

1. Very Much Improved
2. Much improved

CONFIDENTIAL INFORMATION
Auxilium Pharmaceuticals, Inc.
AUX-CC-871-Protocol- 20SEP13

3. Minimally Improved
4. No Change
5. Minimally Worse
6. Much Worse
7. Very Much Worse

7.14.13. End of Study

The end of study is when the last subject completes the Day 95 follow-up visit.

8. ADVERSE EVENTS

Throughout the study, the investigator will monitor each subject for evidence of drug intolerance and for the development of clinical and/or laboratory evidence of an AE. An AE assessment will be made by the investigator on a routine basis throughout the study.

All AEs that occur during the course of the study must be reported in detail on the subject's chart (source document), appropriate CRFs, and on any other report form required by national law.

8.1. Definitions

8.1.1. Adverse Event

An AE is defined as any untoward medical occurrence in a subject or clinical investigation subject administered a pharmaceutical product and which does not necessarily have a causal relationship with this treatment. An AE can, therefore, be any unfavorable and unintended sign (including an abnormal laboratory finding), symptom, or disease temporally associated with the use of a medicinal (investigational) product, whether or not the event is considered causally related to the use of the product. Such an event can result from use of the drug as stipulated in the protocol or labeling, as well as from accidental or intentional overdose, drug abuse, or drug withdrawal. Any worsening of a pre-existing condition or illness is considered an AE. Laboratory abnormalities and changes in vital signs are considered to be AEs only if they result in discontinuation from the study, necessitate therapeutic medical intervention, and/or if the investigator considers them to be clinically significant AEs.

A treatment-emergent AE is defined as any AE with onset or worsening reported by a subject from the time that the first dose of study drug is administered until completion of or discharge from the study (see Section 6.3 for details regarding premature discontinuation).

8.1.2. Serious Adverse Event

Any AE that results in 1 or more of the following is considered a serious adverse event (SAE):

1. Death - Includes death of a fetus due to miscarriage/spontaneous abortion and elective abortion in the subject's partner.
2. Life Threatening Situation - The subject was at immediate risk of death at the time of the event. It does not refer to the hypothetical risk of death if the AE was more severe or was to progress.
3. Inpatient Hospitalization - This includes any new hospital admission during the study or prolongation of an existing hospitalization. The following are not considered serious due to inpatient hospitalization:
 - a. Trips to the ER that do not include a hospital admission

- b. Optional admission not associated with a precipitating medical AE (eg, cosmetic surgery)
 - c. Admission for treatment of a pre-existing condition that has not worsened or had an increase in severity or frequency (eg, cataract surgery)
 - d. Pre-planned treatments or surgical procedures noted in the baseline source documentation
4. Persistent or Significant Disability/Incapacity - Any AE having an outcome that is associated with a substantial disruption of the ability to carry out normal life functions. This includes the inability to work. This is not intended to include transient, interruptions of daily activities.
 5. Congenital Anomaly/Birth Defect in a child of the subject's partner.
 6. Other Medically Important Events - Important medical events that may not result in death, be life-threatening, or require hospitalization may be considered a serious adverse event when, based upon medical judgment, they may jeopardize the subject and/or may require intervention to prevent one of the outcomes listed in 1 through 5 above.

If any serious, life-threatening, or fatal adverse event occurs whether related to study drug or not, the investigator must notify Auxilium within 24 hours by entry into the CRF as an SAE and/or telephone, facsimile, email (see Section 8.5).

8.2. Adverse Event Severity

The severity of the adverse event will be graded using the following definitions:

- Mild - The adverse event is transient and easily tolerated by the subject.
- Moderate - The adverse event causes the subject discomfort and interrupts the subject's usual activities.
- Severe - The adverse event causes considerable interference with the subject's usual activities and may be incapacitating or life-threatening.

8.3. Relationship to Study Drug

The investigator must record the causal relationship of each adverse event in the CRF, and on the serious adverse reporting form (if applicable). An investigator's causality assessment is the determination of whether there exists a reasonable possibility that the study drug caused or contributed to an adverse event.

- Related: There is evidence to suggest a causal relationship between the drug and the adverse event.
- Not related: An adverse event is due to underlying or concurrent illness or effect of another drug or event and is not related to the study drug (eg, has a more likely

alternate etiology and / or a temporal relationship does not suggest a causal relationship).

8.4. Adverse Event Collection Period

All (serious and non-serious) adverse events, whether elicited during study visits or spontaneously reported by the subject, that occur from the time the subject signs the study-specific informed consent form until completion of or discharge from the study will be collected.

Subjects with clinically significant AEs will be followed until the condition resolves or stabilizes, as determined by the investigator.

8.5. Serious Adverse Event Reporting

In the event of an SAE, whether related to study drug or not, the investigator will notify Auxilium within 24 hours of being made aware of the SAE:

[contact]

[contact]

Email: [contact]

8.6. Sponsor Reporting Requirements to Regulatory Authorities

Adverse event reporting, including reporting of suspected unexpected serious adverse reactions (SUSARs), will be carried out in accordance with applicable local regulations.

8.7. Exposure During Pregnancy

An exposure during pregnancy (also referred to as exposure in-utero [EIU]) occurs if:

1. A female becomes, or is found to be, pregnant either while receiving or having been directly exposed to study drug (maternal exposure).
2. A male has been exposed, either due to treatment or environmental, to study drug prior to or around the time of conception and/or is exposed during his partner's pregnancy (paternal exposure).

If any study subject is found to be pregnant during the study the investigator must submit EIU information to Auxilium within 24 hours of awareness of the pregnancy, irrespective of whether an adverse event has occurred.

Follow-up is conducted to obtain pregnancy outcome information on all Exposure in Utero reports with an unknown outcome. Auxilium will follow the pregnancy until completion or until pregnancy termination (eg, induced abortion).

CONFIDENTIAL INFORMATION
Auxilium Pharmaceuticals, Inc.
AUX-CC-871-Protocol- 20SEP13

10. STATISTICAL METHODS AND DETERMINATION OF SAMPLE SIZE

10.1. Statistical and Analytical Plans

10.1.1. Analysis Populations

The intent-to-treat and safety population is defined as all subjects who receive study drug.

10.1.2. Efficacy

For ROM, baseline is before injection on Day 1. Baseline for all other efficacy parameters is the screening visit.

The primary endpoint is the change (degrees) from baseline to the Day 95 follow-up in active forward flexion in the affected shoulder.

Secondary endpoints are:

1. Change from baseline to Day 95 in ASES function sub-scale
2. Change (degrees) from baseline to the Day 95 follow-up in abduction
3. Change from baseline to the Day 95 follow-up in pain with movement using a 11-point VAS
4. Change (degrees) from baseline to the Day 95 follow-up in internal rotation
5. Change from baseline to the Day 95 follow-up in external rotation
6. Change from baseline to the Day 95 follow-up in ASES pain sub-scale
7. Investigator satisfaction with treatment at the Day 95 follow-up
8. Subject satisfaction with treatment at the Day 95 follow-up

10.1.3. Safety

The following variables are safety endpoints.

1. Adverse events: Mapped to preferred term using the Medical Dictionary for Regulatory Activities (MedDRA)
2. Change from screening visit in vital signs
3. Change from screening visit in laboratory tests

10.1.4. Immunogenicity

Immunogenicity variables include anti-AUX-I/anti-AUX-II antibody levels.

10.2. Statistical Methodology

10.2.1. Efficacy

Simultaneous hypothesis tests for all primary and secondary efficacy endpoints will be accomplished with a family-wise 5% significance level by applying a closed hierarchical testing procedure. Under this approach, the first test in the hierarchy that fails to reject its individual hypothesis at the 5% level requires that all hypotheses following the first non-significant hypothesis cannot be tested.

1. For the investigator assessment of improvement with treatment and subject satisfaction with treatment, a Wilcoxon rank sum non-parametric test will be performed to compare active to placebo.
2. Mixed-model ANOVA with factors for treatment group and visit will be performed to compare active to placebo for forward flexion, abduction, internal rotation, and external rotation, ASES function subscale, and pain with movement.

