Efficacy: The primary endpoint is the change (degrees) from baseline to the Day 95 follow-up in active forward flexion in the affected shoulder. Secondary endpoints are: 
• Change from baseline to Day 95 in ASES function sub-scale• Change (degrees) from baseline to the Day 95 follow-up in abduction• Change from baseline to the Day 95 follow-up in pain with movement using a 11-point Visual Analogue Scale (VAS)• Change (degrees) from baseline to the Day 95 follow-up in internal rotation• Change from baseline to the Day 95 follow-up in external rotation• Change from baseline to the Day 95 follow-up in ASES pain sub-scale• Investigator satisfaction with treatment at the Day 95 follow-up• Subject satisfaction with treatment at the Day 95 follow-up	
Safety: The following variables are safety endpoints: 
• Adverse events: Mapped to preferred term using the Medical Dictionary for Regulatory Activities (MedDRA)• Change in vital signs• Change in laboratory tests	

Name of Sponsor/Company: Auxilium Pharmaceuticals, Inc.	
Name of Finished Product: XIAFLEX	
Study Drug: AA4500	
Name of Active Ingredient: collagenase clostridium histolyticum	Study Number: AUX-CC-871
Immunogenicity: Immunogenicity variables include anti-AUX-I/anti-AUX-II antibody levels and neutralizing antibodies to AUX-I and AUX-II.	
Statistical Analyses	
Efficacy: Simultaneous hypothesis tests for all primary and secondary efficacy endpoints will be accomplished with a family-wise 5% significance level by applying a closed hierarchical testing procedure. Under this approach, the first test in the hierarchy that fails to reject its individual hypothesis at the 5% level requires that all hypotheses following the first non-significant hypothesis cannot be tested.	

1. For the investigator assessment of improvement with treatment and subject satisfaction with treatment, a Wilcoxon rank sum non-parametric test will be performed to compare active to placebo.2. Mixed-model analysis of variance (ANOVA) with factors for treatment group and visit will be performed to compare active to placebo for forward flexion, abduction, internal rotation and external rotation, ASES function subscale, and pain with movement.	
Safety: Adverse events will be summarized for the active and placebo groups with the proportion of subjects reporting each event.	

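### The mixed model as written names no treatment-by-visit term and no Day 95 contrast, so read literally it tests a visit average and not the Day 95 endpoint

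*Protocol*

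**What the plan says.** Section 10.1.2 fixes the endpoint at one time point: "The primary endpoint is the change (degrees) from baseline to the Day 95 follow-up in active forward flexion in the affected shoulder". The secondary endpoints listed there are also Day 95 quantities.

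Section 10.2.1 gives the analysis: "Mixed-model ANOVA with factors for treatment group and visit will be performed to compare active to placebo for forward flexion". The same sentence goes on to the other three motions, ASES function and pain with movement. The synopsis repeats it: "Mixed-model analysis of variance (ANOVA) with factors for treatment group and visit will be performed to compare active to placebo for forward flexion". In neither place is a treatment-by-visit term, a visit-specific contrast or the set of visits in the model given. ASES pain is a secondary endpoint but is not in the list of variables analysed this way.

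Section 7.14.4.2 schedules follow-up range of motion as: "Before each injection, Days 8, 29, 50, 64, and at the Day 95 follow-up visit". Section 10.1.2 adds: "For ROM, baseline is before injection on Day 1". That leaves seven post-baseline visits: Days 8, 22, 29, 43, 50, 64 and 95, with Days 22 and 43 measured before the injection. Pain with movement (7.14.5) is collected less often: "During the screening visit; before injection on Days 22 and 43; and at the Days 64 and 95 follow-up visits". ASES function has the same schedule (7.14.4.3.1), so both have four post-baseline visits.

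The tests run at a "family-wise 5% significance level by applying a closed hierarchical testing procedure", in which a failed test stops all later ones.

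**The concern.** A repeated-measures model with treatment and visit as additive factors has one treatment coefficient, common to every visit it includes. That is a different quantity from the Day 95 difference unless the effect is flat over follow-up.

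The design gives no reason to presume a flat effect. Up to three injections are given through Day 43. The Day 8 and Day 22 measurements precede Injection 2, and four of the seven range-of-motion measurements precede Injection 3. Section 7.11 makes retreatment depend on response, and sections 3.1 and 5.1 together describe a condition that can recover spontaneously and subjects who all do home exercises.

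Two errors are possible. If benefit builds with injections, the average understates the Day 95 effect and can lose power. If an early benefit disappears by Day 95, the test can support a Day 95 claim that is untrue. Because forward flexion is the primary endpoint, a wrong answer there would block or release the secondary tests.

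**Working it through.** **Inputs from the protocol.** Section 10.3: 240 evaluable subjects, 3:1 (180 and 60), difference 15 degrees, SD 30, power at least 90%, 20% dropout. Section 7.14.4.2: the seven visits above. Section 10.2.1: 5% level; sidedness is not stated and two-sided is assumed.

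**Assumptions not in the protocol.** The effect trajectories, a within-subject correlation ρ of 0.5 to 0.7, compound symmetry, SD 30 at every visit, and complete data at all seven visits.

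**1. The plan's own figure.** SE = 30 × √(1/180 + 1/60) = 30 × 0.1491 = 4.47. Power = Φ(15/4.47 − 1.96) = Φ(1.39) = 91.8%. Planned enrolment: 240/0.80 = 300. Both figures reproduce, and they reproduce as a comparison at a single time point. The section bases its differences on Study AUX-CC-870, whose primary endpoint was also a single late change, at Day 92 (section 3.5.2).

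**2. What the additive model estimates.** With complete balanced data and a random intercept, the treatment coefficient equals the difference in means averaged over the seven visits. Fitting the model to three simulated data sets gave agreement to about 13 digits. Its standard error is 30 × √((1 + 6ρ)/7) × 0.1491:
- ρ = 0.5: 30 × 0.756 × 0.1491 = 3.38
- ρ = 0.7: 30 × 0.862 × 0.1491 = 3.85

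**3. Four trajectories.** The first three have a Day 95 effect of 15 degrees; the last has none. Effects are listed in the order Days 8, 22, 29, 43, 50, 64, 95.

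| Trajectory | Average effect estimated | Rejection, ρ = 0.5 | Rejection, ρ = 0.7 |
|---|---|---|---|
| Constant 15 | 15.0 | 99% | 97% |
| By thirds with each injection (5, 5, 10, 10, 15, 15, 15) | 75/7 = 10.7 | 89% | 79% |
| Linear from Day 1, 15 × (day − 1)/94 | 15 × (304/7)/94 = 6.9 | 54% | 44% |
| Early, gone by Day 95 (15, 15, 15, 12, 10, 5, 0) | 72/7 = 10.3 | 86% | 76% |

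Each rejection rate is Φ(average/SE − 1.96). For example, the thirds case at ρ = 0.7 is Φ(10.71/3.85 − 1.96) = Φ(0.82) = 79%.

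**4. Sensitivity.**
- For the linear case, ρ from 0.3 to 0.9 gives 69% to 37% power.
- For the thirds case at ρ = 0.3, the SE is 2.83 and power about 97%. Averaging then more than offsets the dilution, but the quantity tested is still not Day 95.
- Under AR(1) with ρ from 0.5 to 0.9, the visits are reweighted. The linear case then gives 7.2 to 7.7 degrees and 79% to 51% power.
- For ASES function and pain with movement, a linear rise over four visits averages (21 + 42 + 63 + 94)/4 ÷ 94 = 59% of the Day 95 effect.

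**The case against.** The protocol lists factors, not model terms. A two-factor ANOVA can include the interaction, and 10.2.1 opens by saying that the tests concern the primary and secondary endpoints, which are defined at Day 95. One can therefore read the model as a tool for a Day 95 comparison, with interaction, contrast and covariance left to the SAP.

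Much of this stands. A reader might infer that the plan has settled on a main-effects model using all visits from Day 8 for every continuous endpoint. The documents do not support that. They do not exclude an interaction or state which visits enter. The questionnaires start at Day 22, and ASES pain is not in the model list.

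A reader might also take 44-54% as the trial's expected power. It is not: the figure needs an effect still rising steadily to Day 95, although the last scheduled injection is at Day 43. The fading case has no documentary basis either and only shows what the test could do. With a constant effect the additive model is correct and more powerful. Subjects not eligible for Injection 2 or 3 need not attend Day 29 or Day 50 (section 7.11.1), so the data will be unbalanced by design and the weights will not be equal.

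What does not stand is that this is only missing detail. The protocol chose to name the factors of its confirmatory model, twice, and that list taken at face value does not produce the stated endpoint. An SAP that follows it literally tests something else; one that adds the interaction and contrast goes beyond what the protocol states.

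**Conclusion.** The point holds in a limited form. The stated model and the stated endpoint do not match on a literal reading, and the text permits two different primary tests. That the literal treatment test is a weighted visit average, equal to the Day 95 difference only under a constant effect, follows from the model and needs no assumed trajectory.

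The size is conditional. Under the assumptions listed, a true Day 95 effect of 15 degrees would be estimated as anything from 6.9 to 15 degrees. Power would run from 44% to 99%, against 92% planned, and one illustrative trajectory gives 76-86% rejection with no Day 95 difference. Other correlations, covariance structures and missing visits change these figures but do not turn the average into a Day 95 contrast.

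**What to change.** In 10.2.1 and in the synopsis, add the treatment-by-visit term to the model. State that the confirmatory test for each endpoint analysed with it is the AA4500 minus placebo contrast at Day 95. The covariance structure can be left to the SAP.

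This costs one sentence in two places, carried into the SAP, and no new data. The statistical price is some power if the effect really is constant: about 92% for the Day 95 contrast against 97-99% for the additive model under the assumptions above. The planned power in 10.3 is kept, because that calculation already describes a Day 95 comparison.
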